9.9. Health Economics

9.9.1. Diabetes Injection Device Experience Questionnaire (DID-EQ)

The Diabetes Injection Device Experience Questionnaire is a newly developed questionnaire to specifically evaluate newer diabetes injection devices (Matza et al. 2016, Matza et al. 2017).

This questionnaire has been developed because all validated device questionnaires were developed specifically for evaluating devices for insulin injections; no validated device experience questionnaire was available that could be used to evaluate devices for injections of GLP-1 RAs.

The DID-EQ will be administered at Week 12 (Visit 6) only, or at the ET visit if early termination occurs prior to Visit 6.

9.9.2. EQ-5D-5L

Generic health-related quality of life will be assessed using the EQ-5D (EQ-5D; EuroQoL Group 2015). The EQ-5D is a standardized 5-item instrument for use as a measure of health outcomes. It provides a simple descriptive profile and a single index value for health status that can be used in the clinical and economic evaluation of healthcare as well as population health surveys. The EQ-5D comprises 5 dimensions of health (mobility, self-care, usual activities, pain/discomfort, and anxiety/depression). The 5L version, introduced in 2005, scores each dimension at 5 levels (no, slight, moderate, severe problems, extreme problems), for a total of 3251 possible health states. In addition, the EQ Visual Analog Scale (VAS) records the respondents' self-rated health status on a vertical graduated (0 to 100) VAS. In conjunction with the health state data it provides a composite picture of the respondents' health status.

The EQ-5D is used worldwide and is available in more than 170 languages. Details on the instrument, and scoring, organizing, and presenting the data collected can be found in the EQ-5D User Guide (EuroQoL Group 2015).

The EQ-5D-5L will be administered at Weeks 0, 36, and 52, and at ET (Visits 3, 9, 11, and ET).

9.9.3. Impact of Weight on Self-Perceptions Questionnaire (IW-SP)

Patients' self-perception related to their body weight will be assessed using the IW-SP (Hayes and DeLozier 2015). The IW-SP is a 3-item questionnaire that has demonstrated validity, reliability, and responsiveness in individuals with T2D and obesity, thereby making it an appropriate tool for the evaluation of weight-loss interventions targeted toward patients with T2D (Hayes and DeLozier 2015). Each item is rated on a 5-point scale ranging from "always" to "never." Total scores for the IW-SP are derived by summing the item scores and dividing by the

number of items. The score can also be transformed to a range from 0 to 100. Higher IW-SP scores correspond to better self-perception (Hayes and DeLozier 2015).

The IW-SP will be administered at Weeks 0, 36, and 52, and at ET (Visits 3, 9, 11, and ET).

9.9.4. Ability to Perform Physical Activities of Daily Living (APPADL)

The APPADL questionnaire contains 7 items that assess how difficult it is for patients to engage in various physical activities considered to be integral to normal daily life, such as walking, standing, and climbing stairs (Hayes et al. 2011; Hayes et al. 2012). Items are scored on a 5-point numeric rating scale, where 5=“not at all difficult” and 1=“unable to do.” A raw overall score is calculated by simply summing the scores of the 7 items, and a transformed overall score is obtained by linearly transforming the raw overall score to a 0 to 100 scale. A higher raw overall score and a lower transformed overall score are indicative of better ability to perform activities of daily living.

The APPADL will be administered at Weeks 0, 36, and 52, and at ET (Visits 3, 9, 11, and ET).

10. Statistical Considerations

10.1. Sample Size Determination

Assuming a screen failure rate of 40%, approximately 3000 patients will need to be screened to attain approximately 1800 patients randomized to the 3 treatment groups (600 patients/groups) in a 1:1:1 ratio for dulaglutide 4.5 mg, 3.0 mg, and 1.5 mg. Assuming 15% dropout, this will result in approximately 510 patients per arm completing 36 weeks of treatment (the primary time point).

The aforementioned sample size provides $\geq 80\%$ power to demonstrate superiority of at least 1 of the investigational dulaglutide doses (4.5 mg or 3.0 mg) to dulaglutide 1.5 mg with respect to the primary endpoint (change from baseline in HbA1c) at Week 36. This sample size is calculated based on the assumption that there is a treatment difference (for either investigational dose) in HbA1c change from baseline of approximately -0.22%, a standard deviation (SD) of 1.1%, and a 2-sided alpha of 0.05.

10.2. Populations for Analyses

Table GBGL.4 defines the populations to be used for analyses.

Table GBGL.4. Populations for Analyses

Population	Description
Entered	All participants who sign informed consent
All randomized	All patients who are randomized
Intent to treat (ITT)	All participants who are randomized and take at least 1 dose of study medication for an assigned treatment arm
Completers	All ITT patients who have an HbA1c measure at Visit 9 (Week 36) regardless of compliance with the protocol, rescue medication, or treatment discontinuation. However, data postrescue and/or posttreatment discontinuation will be excluded
Per protocol (PP)	All ITT patients who meet all of the following criteria: 
 • Have no important protocol deviation that could impact the assessment of the primary endpoint • At least 75% compliant with study drug administration through Week 36 • Complete the treatment period through 36 weeks (Visit 9) • Have a value of the primary efficacy measure (HbA1c) at Visit 9 (Week 36) • Excluding data collected postrescue and/or posttreatment discontinuation

Abbreviation: HbA1c = hemoglobin A1c.

Note: The full list will be defined in the Statistical Analysis Plan.

10.3. Statistical Analyses

10.3.1. General Statistical Considerations

Statistical analysis of this study will be the responsibility of Eli Lilly and Company or its designee. Any change to the data analysis methods described in the protocol will require an amendment ONLY if it changes a principal feature of the protocol. Any other change to the data analysis methods described in the protocol, and the justification for making the change, will be described in the statistical analysis plan (SAP) or the clinical study report (CSR). Additional exploratory analyses of the data may be conducted as deemed appropriate.

Table GBGL.4 defines the populations to be used for analyses.

Efficacy and safety analyses will be conducted in the Intent to Treat (ITT) Population. There will be 2 primary estimands to compare treatment groups in terms of the primary measure of HbA1c change from baseline to Week 36.

One primary estimand will be an efficacy estimand (*de jure* effect) which will use the data collected before initiation of any rescue medication or premature treatment discontinuation to demonstrate the effect of treatment and avoid confounding effects of other antihyperglycemic agents (Little and Kang, 2014). The other primary estimand will be a treatment-regimen estimand (*de facto* effect) which will include data collected after initiation of other antihyperglycemic therapy and/or after premature treatment discontinuation.

The treatment-regimen (*de facto*) estimand is included as primary at the request of the US Food and Drug Administration (FDA). The efficacy (*de jure*) estimand will be considered primary for all other purposes, and will be applied to all efficacy outcomes unless otherwise specified to demonstrate effect of treatment and avoid confounding effects with other antihyperglycemic agents.

Both estimands will be tested at the full significance level of 0.05.

Analyses of safety parameters, except for hypoglycemia events, will be conducted in the ITT Population unless otherwise specified.

Unless otherwise noted, all tests of treatment effects will be conducted at a 2-sided alpha level of 0.05, and CIs will be calculated at 95%, 2-sided. All tests of interactions between treatment groups and other factors will be conducted at a 2-sided alpha level of 0.10.

The baseline will be at the randomization visit (Visit 3). If baseline data are missing, the last nonmissing measurement taken prior to Visit 3 will be used.

Two analysis models will be used for the primary and key secondary continuous efficacy measures. The primary analysis will be mixed-model repeated measure (MMRM) analysis using restricted maximum likelihood (REML). The model will include factors for treatment, pooled country, visit, treatment-by-visit interaction and the baseline as a covariate. For analyses of body weight and FSG, the baseline HbA1c stratification ($\geq 8.5\%$ [69 mmol/mol] and $< 8.5\%$) will be added in this model as a fixed effect. An unstructured covariance structure will be used to model

the within-patient errors. If this model fails to converge, the following covariance structures will be tested in order:

- Toeplitz with heterogeneity
- autoregressive with heterogeneity, by visit
- compound symmetry with heterogeneous variances by visit
- Toeplitz
- autoregressive
- compound symmetry without heterogeneous variances, by visit

The first covariance structure that converges will be used.

The secondary analysis for the primary and key secondary continuous endpoints will be analysis of covariance (ANCOVA). Missing endpoints will be imputed with the last (postbaseline) observation carried forward (LOCF) unless otherwise specified. The percentage of patients achieving target HbA1c <7.0% (53 mmol/mol) will be analyzed using a longitudinal logistic regression with repeated measurements.

For continuous measures, summary statistics will include sample size, mean, SD, median, minimum, and maximum for both the actual and change from baseline measurements. Least-squares mean (LS mean) and standard errors (SEs) derived from the model will also be displayed for the change from baseline measurements. Treatment comparisons will be displayed showing the treatment difference LS mean and the 95% CIs for the treatment differences, along with the p-values for the treatment comparisons.

For categorical measures, summary statistics will include sample size, frequency, and percentages. A Fisher's exact test will be used for treatment comparisons.

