For continuous laboratory analytes, the change from baseline to endpoint will be analyzed using an analysis of variance (ANOVA) on the rank-transformed data, with treatment as a fixed effect. Last observation carried forward (LOCF) will be used to impute missing postbaseline values. For qualitative laboratory analytes, counts and percentages of patients with normal and abnormal values will be analyzed using Fisher's exact test.

Treatment differences in incidence of hypoglycemic episodes will be assessed by Fisher's exact test. Treatment differences in rates of hypoglycemic episodes may be assessed by a likelihood-based approach for repeated measures with negative binomial distribution if data warrant; otherwise, the Wilcoxon rank-sum test will be used.

2. Schedule of Activities

Visit	Screening and Lead-In		Treatment Period										Safety Follow-Up
	1	2	3	4	5	6	7	8	9	10	11	ET ^a	801
Week of Treatment	-2	-1	1	4	8	12	18	26	36	44	52		56
Allowable Deviation (Days)^b	±3	±3		±3	±3	±3	±7	±7	±7	±7	±7		±7
Informed consent	X												
Randomization ^c			X										
Clinical Assessments													
Medical History (General)	X												
CV risk factor history		X											
Gallbladder disease history		X											
Physical	X												
Height	X												
Weight	X		X	X	X	X	X	X	X	X	X	X	X
Vital Signs (3 sitting BP and PR measurements) ^d	X		X	X	X	X	X	X	X	X	X	X	X
Electrocardiogram	X					X ^e	X		X ^e		X ^e	X ^e	X ^e
Adverse events		X	X	X	X	X	X	X	X	X	X	X	X
Concomitant medications	X	X	X	X	X	X	X	X	X	X	X	X	X
Review/record hypoglycemic events			X	X	X	X	X	X	X	X	X	X	X
Remind patients about 6-point SMPG		X						X		X			
Record 6-point SMPG values ^f			X						X		X	X ^g	
Patient summary											X	X	X
Patient Education and Management													
Dispense study diary, instruct in use		X	X			X	X		X	X	X		
Review study diary			X	X	X	X	X	X	X	X	X	X	X
Return study diary			X			X	X		X	X	X	X	X
Diabetes management education ^h		X											
Dispense PG meter/supplies		X	X	X	X	X	X	X	X	X	X		
PG meter, SMPG training ^h		X	X										
Review SMPG values			X	X	X	X	X	X	X	X	X	X	X
Injection training ^h		X	X										
Dispense study drugs and/or injection supplies			X	X	X	X	X	X	X	X			

Schedule of Activities

Visit	Screening and Lead-In		Treatment Period									Safety Follow-Up	
	1	2	3	4	5	6	7	8	9	10	11	ET ^a	801
Week of Treatment	-2	-1	1	4	8	12	18	26	36	44	52	ET	56
Allowable Deviation (Days) ^b	±3	±3		±3	±3	±3	±7	±7	±7	±7	±7		±7
Patient Education and Management (concluded)													

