3.2. Background

Pharmacokinetic (PK)/pharmacodynamics (PD) modeling from original Phase 1-2 dulaglutide studies suggested a dose-dependent incremental benefit with dulaglutide versus currently approved doses on HbA1c and body weight reduction. Phase 2 Study H9X-MC-GBGJ (GBGJ) was recently conducted to assess the safety and efficacy of once weekly dulaglutide 3.0 mg and 4.5 mg in comparison to placebo in 317 patients with T2D treated with metformin monotherapy, with exploratory comparisons to dulaglutide 1.5 mg (the highest dose approved by regulatory agencies). Data from Study GBGJ provided evidence for incremental efficacy of these higher doses of dulaglutide versus 1.5 mg once weekly on glycemic control and body weight reduction, particularly at higher baseline HbA1c levels, with an acceptable tolerability and safety profile at both higher doses. The trial results also suggested stepwise titration of dulaglutide dose was associated with acceptable tolerability of the 2 higher doses.

Further study of higher doses of dulaglutide also was assessed in context with prior dose-finding studies. The currently approved dulaglutide doses (0.75 mg and 1.5 mg once weekly) were selected in the Phase 2/3 Study H9X-MC-GBCF (GBCF), which initially included doses up to 3.0 mg once weekly (Skrivanek et al. 2014). The purpose of the first stage of Study GBCF was to identify an optimal dose using prespecified measures of efficacy (HbA1c and weight) and safety (diastolic blood pressure [DBP] and heart rate [HR]). Following a number of interim data reviews, the Data Monitoring Committee (DMC) recommended discontinuing the dulaglutide 3.0 mg dose because of higher incidence in pancreatic enzyme values above upper limit of normal (ULN) (with or without abdominal pain or suspected pancreatitis), increases in HR, and higher incidence of gastrointestinal (GI) adverse events (AEs) (Skrivanek et al. 2014).

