10.3.4.6. Vital Signs

Descriptive statistics for the actual measurements and changes from baseline for SBP and DBP, PR, and rate-pressure product (RPP; $SBP \times PR / 1000$) will be presented by treatment and visit.

Vital signs will be analyzed using a similar MMRM-based model as that described in Section 10.3.1 for continuous variable analyses.

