The treatment-regimen estimand is included as primary at the request of the US Food and Drug Administration (FDA). The efficacy estimand will be considered primary for all other purposes, and will be applied to all efficacy outcomes unless otherwise specified to demonstrate the effect of treatment and avoid confounding effects with other antihyperglycemic agents.

Each of the estimands will be tested at the full significance level of 0.05.

Analyses of safety parameters will be conducted for the Safety Population unless otherwise specified.

Countries with fewer than 10 randomized patients will be pooled for statistical analyses. Pooled country will be employed for all formal statistical model-based analyses as a block factor unless otherwise denoted.

Unless otherwise specified, all tests of treatment effects will be conducted at a 2-sided alpha level of 0.05, and confidence intervals (CIs) will be calculated at 95%, 2-sided. All tests of interactions between treatments and factors of interest will be conducted at a 2-sided alpha level of 0.10. Multiplicity adjustment will be performed among the hypotheses related to the primary and secondary efficacy endpoints.

The baseline visit will be Visit 3. For all variables, including HbA1c, if baseline data are not available or are missing, the last nonmissing measurement taken up to the first dosing date/time will be used for the baseline measurement. The efficacy measure for the primary analysis is defined as the change from baseline in HbA1c to Week 36 (Visit 9).

For all statistical analyses, missing data will be treated as missing at random for all analyses unless otherwise specified.

The treatment groups mentioned in this document are based on the randomized treatment groups: dulaglutide 4.5 mg, dulaglutide 3.0 mg, and dulaglutide 1.5 mg.

All efficacy and safety data will be summarized by each treatment group at each scheduled visit unless otherwise indicated. Dulaglutide 1.5 mg will serve as the reference treatment for treatment comparison in all efficacy analyses unless otherwise specified.

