6.10.4. Clinical Laboratory Evaluation

Analyses of eGFR, creatinine, and UACR are described in Section 6.10.1.2.9. For other laboratory safety parameters, summaries will be provided in this section. For continuous (numeric) laboratory analytes, including serum lipid parameters (total cholesterol, high-density lipoprotein cholesterol, low-density lipoprotein cholesterol, very-low density lipoprotein cholesterol, and triglycerides), the rank of the change from baseline to endpoint (Week 36 [Visit 9] for primary DBL, Week 52 [Visit 11] for final DBL) will be analyzed as detailed in Section 6.1. For qualitative laboratory analytes, the numbers and percentages of patients with normal and abnormal values will be summarized by treatment.

Each pancreatic enzyme (pancreatic amylase [p-amylase] and lipase) and the maximum postbaseline value will be summarized by treatment in a shift table using $>1 \times \text{ULN}$ and $\geq 3 \times \text{ULN}$ separately for the Safety Population, Safety Population with normal baseline value, and Safety Population with baseline value $>1 \times \text{ULN}$.

An MMRM with pooled country, baseline HbA1c strata, treatment, visit, and treatment-by-visit interaction as fixed effects will be fit to analyze each pancreatic enzyme up to Week 52 (Visit 11). In this model, the log-transformed (post first dose measure/baseline measure) will be

the response variable, and log-transformed baseline measure will be used instead of baseline measure. The variance-covariance structure selection is detailed in Section 6.1.

An ANCOVA model for Week 36 (Visit 9) measurement using LOCF will be fit with the same model as the aforementioned MMRM but removing all terms containing visit.

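### Pulse rate, blood pressure and pancreatic enzymes are measured twice before dosing, but the safety models adjust for only one of the two values; using both would be a free, modest gain in precision.

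*Protocol*

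**What the plan says.** The Schedule of Activities (Protocol Section 2) marks "Vital Signs (3 sitting BP and PR measurements") at Visit 1 and again at Visit 3, and marks pancreatic amylase and lipase at the same two visits. The first injection comes at the end of Visit 3, after the baseline procedures. Protocol 5.1 keeps metformin unchanged through the lead-in, so both values are taken on the same background therapy.

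For analysis there is one baseline. Protocol 10.3.1 sets it, with a fallback: "The baseline will be at the randomization visit (Visit 3). If baseline data are missing, the last nonmissing measurement taken prior to Visit 3" is used instead. SAP 6.1 states "The baseline visit will be Visit 3" and has the same kind of fallback: if that value is absent, "the last nonmissing measurement taken up to the first dosing date/time will be used for the baseline measurement". SAP 6.1.1 adds one corresponding baseline measure as covariate.

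The safety models inherit this rule:

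- **Vital signs.** Protocol 10.3.4.6: "Vital signs will be analyzed using a similar MMRM-based model as that described in Section 10.3.1 for continuous variable analyses". SAP 6.10.3 averages the three readings within a visit, not across visits, and SAP Table GBGL.4 names Visit 3 as the baseline.
- **Pancreatic enzymes.** SAP 6.10.4 models the log ratio of post-dose to baseline value, and "log-transformed baseline measure will be used instead of baseline measure". The Week 36 ANCOVA uses the same terms without visit.

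Nothing in either document averages or jointly models the two pre-dose values.

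**The concern.** A patient's usual pulse rate or lipase level is estimated with error on any one day. A second pre-randomization value carries extra information about that level, cannot be affected by treatment, and is already in the database. Leaving it out makes the confidence intervals for 4.5 mg and 3.0 mg against 1.5 mg wider than the collected data require.

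The measures matter here. Change in pulse rate is a listed secondary safety endpoint. Protocol 3.2 reports that in an earlier dose-finding study the monitoring committee "recommended discontinuing the dulaglutide 3.0 mg dose because of higher incidence in pancreatic enzyme values" above the upper limit of normal, along with heart-rate increases and gastrointestinal events. This trial returns to 3.0 mg and adds 4.5 mg, compared with another dose of the same drug, so the differences to be estimated may be small.

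**Working it through.** **1. The plan's own figure.** Protocol 10.1 gives 600 randomized per arm, 15% dropout, a difference of 0.22, SD 1.1 and at least 80% power.

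- Completers: 600 × 0.85 = 510 per arm.
- SE = 1.1 × √(2/510) = 0.0689; 0.22/0.0689 = 3.19.
- Power per dose: 89.1% at two-sided 0.05, and 83.0% at the 0.025 per dose set in SAP 6.1.4.

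The stated power is reproduced. Nothing below depends on a shortfall in sample size.

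**2. Formula.** Let p be the correlation between Visits 1 and 3, and r the correlation of either with the post-baseline value. Taking r equal for both visits is an approximation: they lie 38 and 36 weeks before Week 36. With outcome variance set to 1, residual variance is

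- Visit 3 as the only baseline: 1 − r²
- Visits 1 and 3 both as covariates: 1 − 2r²/(1 + p)

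The SE ratio is the square root of the second over the first. The equivalent number of completers is 510 divided by the variance ratio.

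**3. Pulse rate, blood pressure, enzymes.** The documents give neither p nor r. The values below are assumptions.

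| p (2 weeks apart) | r (to post-baseline) | Variance ratio | SE reduction | Equivalent completers per arm |
|---|---|---|---|---|
| 0.8 | 0.5 | 0.7222/0.75 = 0.963 | 1.9% | 530 |
| 0.7 | 0.5 | 0.7059/0.75 = 0.941 | 3.0% | 542 |
| 0.8 | 0.6 | 0.6000/0.64 = 0.938 | 3.2% | 544 |
| 0.6 | 0.5 | 0.6875/0.75 = 0.917 | 4.3% | 556 |
| 0.7 | 0.6 | 0.5765/0.64 = 0.901 | 5.1% | 566 |
| 0.8 | 0.7 | 0.4556/0.51 = 0.893 | 5.5% | 571 |
| 0.6 | 0.6 | 0.5500/0.64 = 0.859 | 7.3% | 593 |
| 0.7 | 0.7 | 0.4235/0.51 = 0.830 | 8.9% | 614 |

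The first three rows have the two-week correlation exceeding the longer one by at least 0.2; the gain is then 1.9% to 3.2%. The last two rows have no decay at all. A separate calculation with a stable person effect, a slowly decaying component and measurement noise, at times −2, 0 and 36 weeks, gave SE ratios of 0.960 to 0.984, a reduction of 1.6% to 4.0%.

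**4. What that means in beats per minute.** Assume a residual pulse-rate SD of 8 to 10 bpm (not in the documents). The 95% half-width is 1.96 × SD × √(2/510) = 0.98 to 1.23 bpm. A 2% to 4% reduction removes about 0.02 to 0.05 bpm; 9% removes about 0.09 to 0.11 bpm.

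**5. HbA1c, for comparison.** HbA1c is also taken at Visits 1 and 3, but the two values agree closely. With assumed p of 0.90 to 0.97 and r of 0.3 to 0.7, the same formula gives SE reductions of 0.1% to 2.6%. Entry also restricts Visit 1 HbA1c to 7.5% to 11.0% (inclusion criterion 3). Simulations applying that restriction, under assumed variances and slopes, gave 0.2% to 0.8%.

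**6. Validity.** Both values precede randomized treatment, so adjusting for either or both leaves the randomized comparison unbiased and does not inflate Type I error.

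**The case against.** The strongest reply is that the plan contains no mistake. A single Visit 3 baseline is clear and consistently applied, these safety measures carry no power claim and sit outside the error-controlled hierarchy, and a few hundredths of a beat per minute is unlikely to change a decision. That all stands, and it limits the point to an improvement.

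The vital-sign baseline is also already a mean of three readings. That removes within-visit noise; visit-to-visit variation remains, and only that part can be recovered.

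Visit 1 may differ in conditions: it is not on the Schedule's list of fasting visits, and Protocol 9.4.1.2 also uses it to choose the measurement arm. A shift in level does no harm to a covariate, but a weaker correlation with later values would reduce the gain.

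Three stronger readings are tempting and are not supported:

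- **A gain worth 12% to 25% more patients.** With p = r, the variance ratio is (1 + 2r)/(1 + r)², which gives 12.5% at r = 0.5 and 25% at r = 0.8. This requires readings 2 weeks apart to correlate no better than readings 36 weeks apart, and nothing in the documents supports that.
- **A power problem for the primary endpoint.** The stated power is met, and the HbA1c gain is too small to justify reopening a model specified throughout both documents.
- **A remedy for the findings that stopped 3.0 mg earlier.** The enzyme finding was incidence above the upper limit of normal. SAP 6.10.4 addresses that with shift tables, which a model covariate does not touch. ECG heart rate has only a Visit 1 reading before dosing, so it gains nothing either.

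Body weight is also taken at both visits. It belongs to the controlled hierarchy and is not sized here.

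**Conclusion.** The point holds as a free improvement. For pulse rate, SBP, DBP (and so RPP), lipase and pancreatic amylase, a second pre-dose value is collected and then left unused whenever Visit 3 is present. Using it would lower the SE of the dose differences by roughly 2% to 9% under the assumed correlations, and most plausibly by 2% to 4% if correlation decays over 36 weeks. The direction is secure for any Visit 1 value that adds information beyond Visit 3; the size rests entirely on correlations the documents do not give. There is no bias, no Type I error problem and no case for changing the primary HbA1c analysis.

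**What to change.** In SAP 6.10.3 (vital-sign MMRM) and SAP 6.10.4 (pancreatic-enzyme MMRM and Week 36 ANCOVA):

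- Keep Visit 3 as the baseline for the change score or log ratio, and as a covariate.
- Add the Visit 1 value as a second covariate: the mean of the three readings for vital signs, RPP computed from the Visit 1 values, and the log scale for enzymes.
- If Visit 1 is missing, use the Visit 3 value in its place, so that no patient is lost.
- Specify this before unblinding.

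Leave the HbA1c models, Table GBGL.4, the shift tables and the ECG analyses unchanged. The cost is one added covariate in the named models and a short insertion in each of the two SAP sections, with no new data or visits. Protocol 10.3.1 allows changes that do not alter a principal feature to be made and justified in the SAP, which should cover these safety models without an amendment.
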